8.5.1.1 Standing height

For standing height measurements, European Medicines Agency (EMA) guideline^{[26](#)} should be followed.

A manual for height measurement will be provided to the sites. The use of a calibrated wall mounted stadiometer is mandatory.

Standing height should be measured

- by a trained person blinded to treatment allocation (applicable up to and including visit 16 (week 156) for cohort I) and preferably the same person throughout the trial. Starting from the long-term safety extension (week 156–364), the person performing the height measurement is not required to be blinded, as all subjects are treated with NNC0195-0092 [REDACTED] mg/kg/week.
- preferably by using the same stadiometer
- at the same time (\pm 2 hours, compare to baseline-visit 2) of the day
- without shoes
- with 3 consecutive measurements
- measured in centimetres or inches and rounded to one decimal

The following will be recorded in the eCRF

- date and time of height measurement
- result of height measurement

Confirmation that height measurements have been performed by an independent and trained person should be documented in the subjects medical records.

8.5.1.2 Length measurement

Length should be measured

- in children up to approximately 2 years by preferably the same person throughout the trial
- preferably by using the same length board
- at the same time (\pm 2 hours, compare to visit 2)
- without clothes (including diaper) and shoes
- with 3 consecutive measurements
- measured in centimetres or inches and rounded to one decimal

8.5.1.3 Body weight

Body weight will be measured in kilogrammes (kg) or pounds (lb) with one decimal without shoes and wearing only light clothing.

Body weight should be measured preferably at the same time of the day and by using the same scale throughout the trial, if possible.

8.5.1.4 Body Mass Index (BMI)

BMI will be calculated at the screening visit (visit 1) using the eCRF.

8.5.2 Pubertal status according to Tanner staging

Pubertal status assessed by the Tanner staging in accordance with stages 1-5 [1](#) will be assessed [27](#) according to section [2](#).

The date of menarche will be collected for girls, as applicable.

Female subjects of childbearing potential and male subjects of reproductive age should if applicable be given age appropriate sexual counselling and instructed to use adequate contraceptive methods according to local regulations throughout the trial and until the last visit.

8.6 Assessments for safety

8.6.1 Adverse events

AEs should be assessed according to section [2](#).

Please refer to section [12](#) Adverse Events for more details.

8.6.2 Injection site reactions

Injection site reactions will be evaluated according to section [2](#) and more frequently if deemed necessary by the investigator.

If suspicion of an injection site reaction occurs between site visits, the subject should be instructed to call the site as soon as possible for further guidance. An unscheduled visit may take place “at the investigator’s discretion”.

At all visits injection site reactions will be evaluated by the investigator by visual and manual inspection of injection sites; at randomisation, injection site reactions will be evaluated after trial drug administration.

If an injection site reaction fulfils the criteria for an AE, it should be reported on the AE form according to section [12](#). Additionally, a specific injection site reaction form must be completed in the eCRF.

In the event of an injection site reaction, additional assessments will be performed until resolution, as judged necessary by the investigator. The following results will be recorded in the eCRF:

- Burning

- Pain
- Numbness
- Itching
- Swelling
- Redness
- Induration
- Dimpling (small cavities)
- Macula
- Haematoma
- Bleeding
- Other symptoms/findings

In addition to reporting the injection site reaction on the AE form and on the injection site reaction form, digital photos must be taken of the injection site at the time of identification and hereafter as often as judged by the investigator. Should injection of trial product require more than one injection, all injection sites should be evaluated.

The photos should include trial ID, subject number, date of photo, actual time of photo (24h format) and a ruler for injection site measurement. Copies of all photos will be evaluated by an external dermatologist and subsequently transferred to Novo Nordisk.

The overall process for photo acquisition, transfer, central analysis, reporting of results and archiving is described in the manual prepared by the vendor performing the dermatology review.

8.6.3 Assessment in case of suspicion of severe systemic hypersensitivity

If trial product is discontinued as a consequence of suspicion of acute hypersensitivity reaction to the trial product, blood sampling for assessments of the following should be conducted: anti-NNC0195-0092 antibodies, anti-Norditropin® antibodies, and anti-NNC0195-0092 IgE antibodies and anti-Norditropin® IgE antibodies. Blood sampling should be performed at least 2 weeks after but no later than 4 weeks after the event. GH treatment is not permitted in this period.

In the event of suspected severe systemic hypersensitivity caused by the trial product it is recommended to test for tryptase (total and/or mature tryptase) within 3 hours of the reaction at the local laboratory. Moreover, a baseline tryptase measurement is necessary 1-2 weeks after the event due to inter-individual variation in tryptase baseline concentration. The baseline tryptase sample can be obtained at the same time the antibodies samples are drawn. "Tryptase concentrations (if measured) as well as results of anti-drug antibodies and IgE isotype antibodies should be included in the final SAE report.

8.6.4 Electrocardiogram (ECG)

A standard 12 lead ECG will be taken according to section [2](#).

The investigator will evaluate the ECG recordings and classify them as either: "normal", "abnormal, not clinically significant" or "abnormal, clinically significant".

If the ECG is evaluated as “abnormal, clinically significant” at screening, and judged by the investigator not to be relevant for exclusion of the trial, the finding will be recorded as a concomitant illness.

The ECG results must be dated and signed by the investigator to verify that the data have been reviewed.

If ECG results taken within the last 3 months are available for cohort II and III subjects, these may be used instead. ECG should only be taken in cohort II children if possible with reasonable effort.

8.6.5 X-Ray for bone age assessment

X-Rays of left hand and wrist for bone age (BA) assessment according to the Greulich and Pyle atlas¹⁹ will be taken according to section [2](#). In cohort II bone age assessment should only be performed in children if it is standard practice at the site.

The X-Ray images will be sent to a central imaging laboratory for evaluation. An X-Ray taken within 13 weeks prior to screening can be used as screening data if the image is acquired according to the required standards and available to be sent to the central imaging laboratory.

In order to evaluate eligibility of cohort I and III, the result of the central review of the screening X-Ray image must be available in order to evaluate inclusion criterion [9](#) (cohort I) or inclusion criterion [21](#) (cohort III) (Section [6.2](#)).

FOR GERMANY ONLY: only x-rays taken as normal routine (with regards to dose, frequency and timing of x-rays) during diagnose and thereafter yearly during treatment will be used. No extra x-ray will be performed for the study. **END OF TEXT ONLY APPLICABLE FOR GERMANY.**

The overall process for image acquisition, transfer, central analysis, reporting of results and archiving is described in the Imaging manual prepared by the central imaging laboratory.

8.6.6 Physical examination

A physical examination of the following body systems will be performed according to section [2](#).

- Head, ears, eyes, nose, throat, neck
- Respiratory system
- Cardiovascular system
- Gastrointestinal system, including mouth
- Musculoskeletal system
- Central and peripheral nervous system
- Skin
- Lymph node palpation

The investigator will evaluate the findings from the physical examination and classify them as either: “normal”, “abnormal, not clinically significant” or “abnormal, clinically significant”. At the screening visit, physical examination classified as “abnormal, clinically significant” will be recorded as concomitant illnesses. At the subsequent visits, any clinically significant worsening of physical examination findings from the screening visit will be recorded as an AEs (Section [12.2](#)).

8.6.7 Vital Signs

Vital signs should be assessed seated, if possible, according to section [2](#):

- systolic blood pressure (mm/Hg) seated
- diastolic blood pressure (mm/Hg) seated
- pulse (beats per minute) seated

At screening visit vital signs outside reference ranges which in the investigator judgement are “abnormal, clinically significant” should be recorded as concomitant illness.

At the subsequent visits, any clinically significant worsening or any new clinically significant findings will be recorded as AE (Section [12.2](#)).

8.7 Laboratory assessments

All laboratory analyses in this trial will be performed by the central laboratory contracted by Novo Nordisk unless stated otherwise for a single parameter.

A detailed description of assay methods, reference ranges, procedures for obtaining samples, handling, storage and shipment of the samples (including PK and antibody samples) are specified in the trial-specific laboratory manual provided by the central laboratory.

Samples will be coded in order to keep subject's identity anonymous.

The laboratory provides results to the trial sites in the units preferred by the trial sites while the results that are transferred to the trial database will always be in SI units.

Laboratory results except for biomarkers (IGF-I and IGFBP-3), anti-drug antibodies and PK results will be made available to the investigator by the central laboratory. All pages of the laboratory reports must be reviewed, evaluated, dated and signed by the investigator in a timely manner after receipt. It must be specified by the investigator whether out of range results are clinically significant. Any clinically significant deterioration of a pre-existing condition as well as any new clinically significant signs or symptoms occurring hereafter must be reported as an AE in accordance with section [12.2](#).

The laboratory equipment may provide analyses not requested in the protocol but produced automatically in connection with the requested analyses according to specifications in the laboratory standard operating procedures. Such data will not be transferred to the trial database, but abnormal values will be reported to the investigator. The investigator must review all laboratory results for concomitant illnesses and AEs and report these according to this protocol.

Surveillance of laboratory safety data (with the exception of PK and anti-drug antibody data) will be performed by a medical specialist at least every 3 months based on safety surveillance reports. The medical specialist will evaluate the laboratory safety data and look for potential safety signals or issues (safety surveillance). If a signal or alert is identified, the medical specialist will immediately inform the chairman of the Novo Nordisk safety committee.

All laboratory samples except antibody samples will be destroyed at the latest at the completion of the clinical trial report (CTR). Antibody samples may be retained until drug approval by FDA and EMA. The retained antibody samples may be used for further characterisation for antibody response towards drug if required by health authorities or for safety reasons see section [24.2](#).

The use of topical anaesthetics (e.g. numbing cream) for blood sampling should be according to local practice.

Blood sampling volume

To consider the paediatric population included in the trial the volume of blood samples will be minimised, in accordance with the EMA [28](#) and FDA [29](#) guidelines. Instructions will be provided to the trial sites regarding blood sampling volume and prioritisation of samples. If trial sites as part of routine assessments perform additional blood draws, they must ensure that the blood sampling volume will not exceed the above requirements.

Especially for cohort II, it is recommended not to attempt venepuncture more than 3 times for the purpose of obtaining sufficient blood sampling.

[Table 8-1](#) lists the blood volume required to be collected for the scheduled trial blood samples.

Table 8-1 Approximate blood volumes collected during the trial

Visit (cohort I)	mL (cohort I)	Visit (cohort II and III)	mL (cohort II and III)
Visit 1(-3- 2 weeks)	11.0	Screening visit	11.0
Visit 2	5.0	Visit 2	5.0
Visit 3	5.0	NA	NA
Visit 4	8.0	NA	NA
Visit 5	11.6	NA	NA
Visit 6	8.0	NA	NA
Visit 7	11.6	NA	NA
Visit 8	5.0	NA	NA
Visit 9	12.0	NA	NA
Visit 10	5.0	NA	NA
Visit 11	12.0	NA	NA
Visit 12	5.0	NA	NA
Visit 13	12.0	NA	NA
Visit 14	5.0	NA	NA
Visit 15	12.0	NA	NA
Visit 16 ⁽¹⁾	3.0	NA	NA
Visit 18	11.0	Visit 18	11.0
Visit 20	11.6	Visit 20	11.6
Visit 22	11.0	Visit 22	11.0
Visit 24	11.6	Visit 24	11.6
Visit 26	11.0	Visit 26	11.0
Visit 28	11.6	Visit 28	11.6
Visit 30	11.0	Visit 30	11.0
Visit 32	11.6	Visit 32	11.6
Visit 34	11.0		
Visit 36	11.6		
Visit 38	11.6		
Total volume collected during the trial	221.6²	Total maximum volume collected during the trial	106.4
	Up to 255.8³		

¹ Subjects that discontinue early should perform the follow-up visit at least 7 days after discontinuation.

² Only applicable for subjects completing the trial after 364 weeks.

³ Only applicable for subjects continuing until NNC0195-0092 is available for prescription for children with GHD, or until August 2024, at the latest.

If available, local guidelines on blood sampling volumes for children should be followed otherwise the blood volume to be collected at each blood sampling visit should not exceed 1% of the subject's total blood volume. The blood volume to be collected over a period of 4 weeks should not exceed 3% of the subject's total blood volume [Table 8-2](#).

For children weighing less than 15 kg blood sampling at visits requiring higher blood volumes than allowed, the blood sampling can be split into two different occasions with maximum one week apart. The sampling conditions (fasting or non-fasting) and timing of sampling in relation to study drug administration should always be followed.

Table 8-2 Estimated total blood volumes and maximum blood sampling volumes according to EMA guidelines.

Body weight kilogrammes (kg)	Total blood volume 80 mL/kg	Maximum blood sampling volume at any single occasion (mL) 1%	Maximum blood sampling volume within 28 days (mL) 3 %
5	400	4	12
10	800	8	24
15	1200	12	36
20	1600	16	48
25	2000	20	60
30	2400	24	72
35	2800	28	84
40	3200	32	96
45	3600	36	108
50	4000	40	120

Investigator must ensure that the collected blood volume is appropriate in relation to weight of the subject. In case of re-sampling only the affected blood sample(s) should be collected and the investigator must ensure that the blood volume limit is not exceeded.

8.7.1 Biochemistry

The following will be assessed according to section [2](#).

- Alanine Aminotransferase (ALT)
- Aspartate Aminotransferase (AST)
- Bilirubin (total)

- Calcium (total)
- Creatinine
- Phosphate
- Potassium
- Sodium
- Chloride
- Uric acid
- Total protein
- Albumin
- Creatine Kinase
- Alkaline Phosphatase (AP)

GFR (glomerular filtration rate) estimated a derived variable based on s-creatinine and multiplication factors for race and sex, will be calculated by the central laboratory.

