In the main trial period of the study sixty (60) subjects will be randomised in a 1:1:1:1 (████ mg/kg/week NNC0195-0092: ████████ mg/kg/week NNC0195-0092: ████████ mg/kg/week NNC0195-0092: ████████ mg/kg/day Norditropin® FlexPro®) manner to receive either NNC0195-0092 or

Norditropin® FlexPro®. After week 52 all subjects in the NNC0195-0092 arm are switched to [REDACTED] mg/kg/week. After week 156 all subjects on Norditropin® FlexPro® are switched to NNC0195-0092 ([REDACTED] mg/kg/week).

In the long-term safety extension trial period subjects from two additional age groups will be enrolled, cohort II (< 2 years and 26 weeks at screening) and cohort III (> 9 years (girls)/>10 years (boys) and ≤ 17 years at screening) and will be treated with once-weekly NNC0195-0092 ([REDACTED] mg/kg/week). They will start treatment at visit 2 where after they will continue the visit schedule for the long-term safety extension (visit 17 and onwards). Subjects in cohorts II and III will be treated with NNC0195-0092, [REDACTED] mg/kg/week until latest August 2024 (expected last end-of-treatment visit for cohort I) (for details, see Section [8.3.3](#)). As recruitment of subjects from these age groups may be challenging, enrolment of subjects naïve and non-naïve to GH treatment until 4 months prior to expected last end-of-treatment visit for cohort I is possible, unless recruitment has already been completed.

Data from the trial for cohort I will be analysed when all subjects have completed the 26, 52, 104 and 156 and 364 weeks of treatment. For subjects continuing treatment until NNC0195-0092 is available for prescription in their country or August 2024 at the latest, the additional data collected between week 364 (visit 32) and the end-of-treatment visit (visit 38) will be analysed additionally. Further interim reporting may be performed including cohort II and III in association with marketing authorisation application or in connection with Health Authorities e.g. FDA, EMA and PMDA requirement for/during the regulatory review. Final analysis will take place when all subjects have completed the trial.

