Subjects in the weekly and daily dosing arms will be trained by the site staff in the use of the pen-injector and how to inject themselves with the trial drug. The first dose will be administered by the subject (at visit 2) under supervision of the site staff (Sections [2](#) and [8.10](#)). The subsequent doses will be administered by the subject at home. The subject will be instructed to inject themselves in the thighs, dorsogluteal region (upper buttocks), upper outer triceps area (back of upper arm) or in the abdomen with rotation within these body areas for each injection. Body weight will be measured at all visits during the treatment period and will be used for dosing calculation. The maximum treatment duration for a single subject is 364 weeks. No maximum calculated dose is specified.

Subjects with body weight above 50 kilograms (110 pounds) who are randomised to NNC0195-0092 will need to have two injections at dosing due to the injection pen limitations. The volume of the injections should be equal, and the injection sites should be different.

Time of injections:

- Applicable for cohort I until visit 15: NNC0195-0092 should be injected in the morning no later than 10 AM to ensure consistency of PK/PD with previous trials. The trial drug can be injected by 12 PM (noon) on the clinic visit days. Trial drug must not be administered in the morning before relevant visit procedures have been performed (Sections [8.7.6](#) and [8.7.8](#)). If a subject forgets to inject the dose in the morning, the subject must take the dose as soon as possible during the same day.
- Applicable for cohort I subjects after visit 15: NNC0195-0092 can be injected anytime during the dosing day.
- Applicable for cohort II and III: NNC0195-0092 can be injected anytime during the dosing day.
- Injections with NNC0195-0092 the day before blood sampling for anti-NNC0195-0092 antibodies must occur at least 12 hours prior to planned blood sampling.
- If the dose is not administered on the planned dosing day, the dose must then be administered as soon as possible after the missed planned dosing day.
- If the dose cannot be administered within 2 days after the planned dosing day, the dose should be skipped. The next dose afterwards should be taken on the originally planned weekday compared to baseline (randomisation).

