8.4 Subject related information

8.4.1 Demography

Information about date of birth and sex will be captured in IWRS according to the local regulations. Race and ethnicity will be recorded in the eCRF according to the local regulations.

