The scores of the PROs ranges from 0-100. A lower score indicates a better health state.

For subjects switching from Norditropin® to NNC0195-0092 GH-PPQ (The Growth Hormone Patient Preference Questionnaire-Parent/Guardian) at week 160 will be analysed using descriptive statistics. Answers are scored on a 5 levels scale from 'Not at all' to 'Extremely' or from 'Never' to 'All of the time'.

Safety

The following will be described using descriptive statistics for up to the end of the extension until NNC0195-0092 is available for prescription or August 2024 at the latest:

Incidence of technical complaints, including injection site reactions

Changes from baseline to week 26, 52, 104, 156, 260, 364 (the latter for cohort I) and every year until the end of the extension until NNC0195-0092 is available for prescription for children with GHD or August 2024 at the latest in physical signs and vital signs

Changes from baseline to week 26, 52, 104, 156, 260, 364 (the latter for cohort I) and every year until the end of the extension until NNC0195-0092 is available for prescription for children with GHD or August 2024 at the latest in clinical safety laboratory parameters, including haematology,

biochemistry, hormones (e.g. fasting serum cortisol, thyroid function test), lipids, fasting glucose, fasting insulin, and HbA1c levels

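### The eGFR description in Section 8.7.1 names no height or age term, so growth-related creatinine rises would appear as declining kidney function, mainly after week 156 when no control arm remains

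*Combined protocol and SAP*

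**What the plan says.** Section 8.7.1 lists creatinine as a biochemistry analyte. It then adds estimated GFR as "a derived variable based on s-creatinine and multiplication factors for race and sex", which "will be calculated by the central laboratory". No formula, constant or exponent appears. Section 8.7 refers to a laboratory manual for "A detailed description of assay methods, reference ranges, procedures for obtaining samples, handling, storage and shipment of the samples"; it does not say that the manual holds the eGFR equation.

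Section 17.4.3 plans descriptive summaries, "Changes from baseline to week 26, 52, 104, 156, 260, 364 (the latter for cohort I) and every year until the end" of the added extension, "in clinical safety laboratory parameters, including haematology", biochemistry and other panels. eGFR is not named there; it enters only as part of biochemistry. Section 8.7 also sends routine laboratory results to the investigator, who must judge out-of-range values, and to a medical specialist at least every 3 months.

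On duration, Section 5.3 says "The maximum treatment duration for a single subject is 364 weeks", while Table 2-4 lets cohort I continue to week 442 at the latest. On control, Section 5.1 says "After week 156 all subjects on Norditropin® FlexPro® are switched to NNC0195-0092". Cohorts II and III receive only the weekly product. Section 12.7.2 ends data monitoring committee activity after the safety extension.

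**The concern.** The trial gives growth-promoting treatment to children and follows cohort I for 364/52 = 7 years or longer. A kidney measure whose only time-varying input is creatinine cannot separate two causes of a creatinine rise: a larger child, or a kidney that filters less. If creatinine rises with body size, a healthy, well-growing child shows a steady fall in eGFR.

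Two uses are exposed. The change-from-baseline summaries would carry a downward trend that a reader could take for a drug effect. The investigator and the medical specialist would see falling values in individual children with no stated means of allowing for growth. Both problems grow with time on trial. They are largest once the daily arm has switched and the data monitoring committee has stopped.

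**Working it through.** The plan states no eGFR figure, so there is nothing to reproduce. The check is algebra plus labelled assumptions.

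**Inputs from the documents.** eGFR depends on creatinine, race and sex (8.7.1). Summary times run to week 364 and yearly after that (17.4.3). The daily arm ends at week 156 (5.1). The delta of 3.8 cm/year (17.1) serves only as a large-case difference in height velocity between arms.

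**Assumptions, not in the documents.** Exponent b of 1.0 to 1.2; baseline height of 80, 95 or 120 cm; growth of 5, 7 or 10 cm/year; constant true GFR; creatinine proportional to height in steps 2 to 4.

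**Step 1: within-child change.** As described, eGFR = K × Scr^(−b) × race × sex. Race and sex cancel, so eGFR_t/eGFR_0 = (Scr_t/Scr_0)^(−b). For b = 1.0 and b = 1.2:
- creatinine up 0%: no change
- up 10%: −9.1% and −10.8%
- up 30%: −23.1% and −27.0%
- up 50%: −33.3% and −38.5%

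**Step 2: drift from growth.** With b = 1, the change is H_0/(H_0 + g × w/52) − 1, where g is growth in cm/year and w is the week. For example, 95 cm growing 7 cm/year to week 156 gives 95/(95 + 21) − 1 = −18.1%.

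| Baseline height, growth | Week 26 | Week 52 | Week 156 | Week 364 |
|---|---|---|---|---|
| 120 cm, 5 cm/year | −2.0% | −4.0% | −11.1% | −22.6% |
| 95 cm, 7 cm/year | −3.6% | −6.9% | −18.1% | −34.0% |
| 80 cm, 7 cm/year | −4.2% | −8.0% | −20.8% | −38.0% |
| 80 cm, 10 cm/year | −5.9% | −11.1% | −27.3% | −46.7% |

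The last cell is not carried into the stated range, because it would need 70 cm of growth over seven years. The week 364 range therefore uses 5-7 cm/year.

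**Step 3: what remains between randomised arms.** For height velocities of 10 and 6.2 cm/year (difference 3.8), the relative eGFR difference is (H_0 + 10y)/(H_0 + 6.2y) − 1, with y in years. Across the three baseline heights this is 1.5-2.3% at week 26, 3.0-4.4% at week 52 and 8.2-11.6% at week 156. For 10 and 9 cm/year it is 0.4-0.6%, 0.8-1.1% and 2.0-2.8%.

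**Step 4: with height in the numerator.** The ratio becomes (H_t/H_0)/(Scr_t/Scr_0). It equals 1 at every visit when creatinine is proportional to height, so the drift is 0% by construction.

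**Step 5: if creatinine is not proportional to height.** Take assumed values of 95 to 150 cm and creatinine 0.35 to 0.60 mg/dL. The height-based ratio is (150/0.60)/(95/0.35) = 0.92, an 8% fall. Without height it is 0.35/0.60 = 0.58, a 42% fall. If creatinine reaches only 0.50, the results are an 11% rise with height and a 30% fall without it. A height term reduces the artefact but need not remove it.

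**Step 6: is height available?** In Table 2-1 every biochemistry visit (1, 4, 5, 6, 7) also has height. Tables 2-2, 2-3 and 2-4 show height at every treatment visit, and Table 2-5 shows height or length throughout. The biochemistry rows of Tables 2-2 and 2-3 are not visible in the text read. Any biochemistry at a treatment visit there still has a height beside it.

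**The case against.** The strongest reply is that Section 8.7.1 gives a one-sentence description, not the equation. A height or age term may sit in laboratory documentation that is not public, so it is unstated rather than shown to be absent. That stands. A reader might infer that an adult equation is in use, but the documents do not establish it. They do name the inputs, and the sentence as written leaves out body size.

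Second, the creatinine rise is a physiological assumption, since the documents contain no creatinine data. That also stands, which is why the size is a range that includes zero.

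Third, a reader might infer that eGFR cannot serve as a kidney safety measure at all. The documents do not support that. Creatinine is reported and reviewed separately, and eGFR is not an endpoint, an eligibility criterion or a discontinuation criterion. The daily arm also gives a concurrent comparison to week 156. Every arm receives growth hormone, so step 3 leaves little drift between arms unless height velocity differs greatly. This protection helps only a reader who compares arms; change within one arm still drifts. A large true loss would not be hidden either: with b = 1, doubled creatinine halves eGFR.

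Fourth, a reader might infer that the race factor is missing in some countries. Section 8.4.1 says "Race and ethnicity will be recorded in the eCRF according to the local regulations", which does not show that race is missing anywhere.

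**Conclusion.** The point holds in a limited form. As described, eGFR moves within a child only through creatinine, and nothing in the description separates growth from loss of function. The resulting false decline is about 4-11% at week 52 and 11-27% at week 156 (5-10 cm/year), and about 23-38% at week 364 (5-7 cm/year). These figures assume creatinine proportional to height, constant true GFR, b = 1 and baseline heights of 80-120 cm. If creatinine does not rise, the decline is zero.

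The exposure is mainly in the long-term safety extension and beyond, including cohorts II and III, where no concurrent control exists, and in individual safety review throughout. The primary height velocity analysis is unaffected. The sentence should still be corrected, because it specifies a derivation poorly suited to this population and the data for a better one are already collected.

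**What to change.** Replace the sentence in Section 8.7.1 with a named paediatric equation, written out in full, that uses serum creatinine and the height or length from the same visit. Add a fallback to the nearest on-site measurement, because Section 27.3 allows height to be measured only on site during an emergency. Recalculate all earlier eGFR values from recorded creatinine and height, so that the change-from-baseline series in Section 17.4.3 rests on one equation. If the central laboratory already uses a height term, correct the description to say so; no recalculation is then needed.

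The cost is a change to the laboratory derivation or a programming step at the sponsor, with no new sample or visit. The downside is that eGFR values already reported to sites will not match the recalculated series, so the clinical trial report should explain the difference.
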